3. OBJECTIVES AND ENDPOINTS

The objectives and corresponding endpoints are provided in [Table 4](#).

Note: Due to the adaptive nature of Part III, additional cohorts, which are not described in this protocol, may be added in the study (see [Appendix 6](#), [Appendix 7](#), [Appendix 8](#), and [Appendix 9](#)). For a rationale, see [Appendix 9](#).

Table 4 Objectives and Endpoints

Objectives	Endpoints
Primary	
All Parts (Dose Escalation [Part I] and Dose Expansion [Part II and Part III])	
To evaluate the safety, tolerability, maximum tolerated dose (MTD) and/or recommended Phase 2 dose (RP2D) (Part I only) of RO7296682 when administered in combination with atezolizumab.	
 • Nature and frequency of adverse events (AEs) with severity determined according to NCI CTCAE v5.0 • Nature and frequency of dose-limiting toxicities (DLTs) in Part I
Primary (Dose Expansion Part II and Part III)	
To evaluate the preliminary anti-tumor activity of RO7296682 when administered in combination with atezolizumab.	
 • Objective response rate (ORR) according to RECIST v1.1
Secondary (Dose Escalation, Part I)	
To evaluate the preliminary anti-tumor activity of RO7296682 when administered in combination with atezolizumab.	
 • ORR according to RECIST v1.1
Secondary (Dose-Escalation [Part I] and Dose Expansion [Part II and Part III])	
To further characterize the anti-tumor activity of RO7296682 when administered in combination with atezolizumab.	
 • Disease control rate (DCR) defined as response rate (RR) and stable disease (SD) • Duration of response (DoR) • Progression-free survival (PFS) 
All according to RECIST v1.1
 
 • Overall survival (OS), if data are mature at the time of analysis
To investigate the pharmacokinetic (PK) profile of RO7296682 and atezolizumab after administration of RO7296682 in combination with atezolizumab.	
 • PK profiles and parameters derived for RO7296682 and atezolizumab, as appropriate, including but not limited to: 
 ○ Area under the curve (AUC) ○ Minimum (C_{\min}) and maximum (C_{\max}) concentration ○ Time of maximum concentration (T_{\max}) ○ Volume of distribution at steady-state (V_{ss}) ○ Half-life ($t_{1/2}$)

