8.1 EFFICACY ASSESSMENTS

8.1.1 Tumor and Response Evaluations

Tumor response will be evaluated according to both RECIST v1.1 ([Appendix 13](#)) and immune RECIST (iRECIST, [Appendix 14](#)). Tumor lesions will be assessed at screening and every 8 weeks (\pm 7 days) after first dose (i.e., C1D1) -regardless of any treatment delays - for the first year, and then every 12 weeks (\pm 7 days) thereafter until disease progression. The visit at which a response assessment shows progressive disease may be used as the discontinuation visit. For participants who discontinue treatment for any other reason than disease progression: an end of study CT/MRI scan is only to be performed if it was done \geq 28 days prior to this day. In addition, a CT/MRI scan to be performed at the safety follow-up visit.

Response will be assessed by the Investigator based on physical examinations and CT scans (or MRI) of chest, abdomen, and pelvis as defined in the SoAs (Section 1.3). CT scans of the neck should be included, if clinically indicated. Ultrasound and x-rays are not acceptable for monitoring target lesions. All measurable disease must be documented at screening and re-assessed at each subsequent tumor evaluation.

A CT or MRI scan (with IV contrast unless contraindicated) of the head must be performed at screening to assess CNS metastasis. An MRI scan of the brain is required to confirm or refute the diagnosis of CNS metastases at baseline in the event of an ambiguous CT scan. Patients with untreated or actively progressing CNS metastases are not eligible for the study (see Section 5.2). Stable brain metastases must be evaluated at each tumor assessment with the same radiographic procedure as the baseline. Patients without brain metastases do not need brain scans for tumor assessment unless clinically warranted.

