9.4.2 Efficacy Analyses

The primary and secondary efficacy analyses listed in [Table 14](#) will include all participants in the efficacy population with participants grouped according to dose cohort (and schedule if applicable) within each study part.

Table 14 Efficacy Statistical Analysis Methods

Endpoint	Statistical Analysis Methods
According to RECIST Version 1.1 criteria (Appendix 13) and iRECIST (Appendix 14) 
• Objective response rate (ORR)• Disease control rate (DCR)• Duration of response (DoR)• On treatment progression free survival (PFS)	No formal statistical model and no formal hypothesis testing are planned in this study. Tumor response data will be reported using descriptive statistics. Response data will be listed. Participants with missing or no response assessments will be classified as not evaluable unless there is documented clinical deterioration, in which case participant will be classified as non-responders. Reasons for the non-evaluability will be summarized (e.g., withdrawal of consent, study discontinuation because of AE or physician decision). ORR and DCR will be summarized by using relative frequencies and 90% confidence interval (CI). Duration of response and PFS (on-treatment) will be summarized by using time-to-event analyses and Kaplan-Meier curves.
• Overall Survival (OS) (if available)	OS data may be tabulated and summarized using time-to-event analyses and Kaplan-Meier curves if data are collected and mature. Summaries will be carried out by cohort (and schedule if applicable) separately for each part.

Objective response rate (ORR) is determined as the rate of participants with an overall response of CR or PR. DCR is determined as the rate of participants with an overall response of either CR, PR, or SD rate. ORR and DCR will be derived for RECIST v1.1 and will be based on Investigators' assessment. Objective response (OR) is defined as a CR or PR as determined by the Investigator. For this protocol, confirmation of response is required at least 4 weeks after a first response occurred. To classify a response as SD, measurements will have to be classified as stable (according to RECIST v1.1) at least once after study entry at a minimum of 6 weeks after study entry. Participants with missing or no response assessments will be classified as not evaluable unless there is documented clinical deterioration, in which case participants will be classified as non-responders.

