DoR will be calculated for participants who have a best overall response of CR or PR and defined as the time from first occurrence of a documented OR until the time of

documented disease progression or death (death within 30 days from last study treatment) from any cause, whichever occurs first. Censoring methods will be the same as the one applied for progression-free survival (PFS; on-treatment).

PFS on treatment will be defined as the time from study treatment initiation (C1D1) to the first occurrence of documented disease progression (based on RECIST v1.1 Investigator's assessment) or death from any cause, whichever occurs first. For participants who do not have documented progressive disease or death (within 30 days from last study treatment) during the study, PFS will be censored at the day of the last tumor assessment. Participants without any post baseline assessments or with all post-baseline assessments having unknown result/response but known to be alive at the clinical cut off for the analysis will be censored at the date of study treatment initiation plus one day.

Sensitivity analyses of response endpoints (ORR, DCR, DoR, and PFS) may include the evaluation of response according to iRECIST and the evaluation of response from an independent centralized review.

OS is defined as the time from the first dose of study treatment to the time of death from any cause. Participants who are still alive at the time of analysis will be censored at the time of their last study assessment (for active participants) or at the last date known alive (for participants in follow-up).

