a If a CR is truly met at first time point, then any disease seen at a subsequent time point, even disease meeting PR criteria relative to baseline, makes the disease PD at that point (since disease must have reappeared after CR). Best response would depend on whether minimum duration for SD was met. However, sometimes 'CR' may be claimed when subsequent scans suggest small lesions were likely still present and in fact the patient had PR, not CR at the first time point. Under these circumstances, the original CR should be changed to PR and the best response is PR.

2 Special Notes on Response Assessment

When nodal disease is included in the sum of target lesions and the nodes decrease to 'normal' size (< 10 mm), they may still have a measurement reported on scans. This measurement should be recorded even though the nodes are normal in order not to overstate progression should it be based on increase in size of the nodes. As noted earlier, this means that participants with CR may not have a total sum of 'zero' on the case report form (CRF).

Participants with a global deterioration of health status requiring discontinuation of treatment without objective evidence of disease progression at that time should be reported as "symptomatic deterioration." Every effort should be made to document objective progression even after discontinuation of treatment. Symptomatic deterioration is not a descriptor of an objective response: it is a reason for stopping study therapy. The objective response status of such participants is to be determined by evaluation of target and non-target disease as shown in [Table 1](#), [Table 2](#), and [Table 3](#).

For equivocal findings of progression (e.g., very small and uncertain new lesions; cystic changes or necrosis in existing lesions), treatment may continue until the next scheduled assessment. If at the next scheduled assessment, progression is confirmed, the date of progression should be the earlier date when progression was suspected. In studies where participants with advanced disease are eligible (ie, primary disease still or partially present), the primary tumor should be also captured under target or non-target lesions as appropriate. This is to avoid wrong assessments of complete overall response by statistical programs while the primary is still present but not evaluable.

References

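### PFS counts death from any cause in its definition, but its censoring sentence drops deaths more than 30 days after last dose, while progression has no matching limit

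*Combined protocol and SAP*

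**What the plan says.** Section 9.4.2 measures PFS from C1D1 to the first investigator-documented RECIST v1.1 progression "or death from any cause, whichever occurs first". No window is attached to either component. The following sentence sets the censoring: for participants without documented progression "or death (within 30 days from last study treatment) during the study, PFS will be censored at the day of the last tumor assessment".

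DoR is worded differently. Its end point is "documented disease progression or death (death within 30 days from last study treatment) from any cause, whichever occurs first", so the window sits inside the definition. DoR takes its censoring from PFS.

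A third rule covers participants with no post-baseline assessment, or only unknown results. Those "known to be alive at the clinical cut off for the analysis will be censored at the date of study treatment initiation" plus one day.

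The labels differ. Table 14 has "On treatment progression free survival (PFS"; Table 4 in Section 3 has "Progression-free survival (PFS".

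On scanning, Section 8.1.1 schedules tumor assessments until progression and adds: "In addition, a CT/MRI scan to be performed at the safety follow-up visit". Sections 4.1.1 and 8.11.4 place that visit at 135 (±30) days after last dose.

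**The concern.** Two programmers working from Section 9.4.2 could produce different PFS event counts from the same data. One would follow the definition and count every death; the other would follow the censoring sentence and drop late ones.

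Taken literally, the censoring sentence also gives neither any-cause PFS nor a PFS with one window for both components. Late progression counts and late death does not. Censoring a death at an earlier scan is potentially informative, because participants who die off treatment are unlikely to have the same prognosis as those still being followed.

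The stakes are limited. Section 9.1 plans no hypothesis test, and PFS and DoR are secondary in all parts. They do appear in Section 9.5 among the endpoints that may overrule the non-binding futility rules. The sensitivity analyses foreseen in Section 9.4.2 (iRECIST and central review) do not address which deaths count.

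**Working it through.** The plan gives no PFS event count, rate or power, so there is no figure of its own to reproduce.

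**1. One participant, two answers.** Last dose day 200; last scan, without progression, day 224; death without progression day 245.
- Days from last dose to death: 245 − 200 = 45, which is more than 30.
- Definition: event at day 245.
- Censoring sentence: censored at day 224.
- Had the participant lived and progression been first seen at the safety follow-up scan (200 + 135 = day 335), it would be an event under both sentences.

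**2. Length of the mismatch.** Deaths stop counting at day 30 after last dose. The safety follow-up scan falls at day 135, or 105 to 165 with its window.
- Nominal: 135 − 30 = 105 days.
- With the visit window: 105 − 30 = 75 to 165 − 30 = 135 days.
- If scans continue to progression, as Section 8.1.1 can be read, it is longer.

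**3. The gap.** Table 13 keeps in the efficacy population participants who stop for progression before any on-study scan. Suppose one receives a single dose on day 1, is never scanned again and dies on day 100 without RECIST-documented progression.
- Definition: event at day 100.
- Censoring sentence: the death is 99 days after last dose, so outside the window, and there is no post-baseline assessment at which to censor.
- C1D1-plus-one-day rule: does not apply, because the participant is not known to be alive.

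**4. Direction, by hand Kaplan-Meier.** Take 20 participants with 8 events by week 16. One further participant, last scanned at week 16, later dies outside the window. Four others have events between weeks 16 and 26, and there is no other censoring. As written, 26-week PFS is 12/20 × 7/11 = 38.2%.
- Death at week 24, counted: 7/20 = 35.0%. The written rule is higher.
- Death at week 30, counted: 8/20 = 40.0%. The written rule is lower.

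**5. Size, under assumed rates.** The PFS simulation used 27 scenarios of 200,000 participants:
- median time to progression 3, 4 or 6 months;
- stopping treatment for other reasons 3, 5 or 10% per month;
- progression-free death off treatment 0.05, 0.10 or 0.20 per month, and 0.01 on treatment;
- scans as in Section 8.1.1, with a 24-month cut-off.

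Every simulated participant has at least one post-baseline scan, so the gap in step 3 is not included. The DoR grid of 27 used medians of 6, 9 or 12 months and off-treatment death of 0.02, 0.05 or 0.10 per month (0.005 on treatment). The table gives the written rule minus all-deaths, in percentage points.

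| Estimate | Scans stop after safety follow-up | Scans continue to progression |
|---|---|---|
| 26-week PFS | +0.1 to +6.0 (median 1.1) | +0.5 to +7.6 (median 1.9) |
| 52-week PFS | −1.3 to +7.2 (median 0.6) | +0.5 to +10.2 (median 2.4) |
| 52-week DoR | +0.1 to +9.4 (median 1.9) | +0.7 to +12.0 (median 3.3) |

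Repeat runs move the extremes by a few tenths of a point; one put the largest 52-week PFS shift at 10.8. With scans stopping, 52-week PFS moves up in 18 scenarios, down in 8 and not at all in 1. Median PFS is unchanged in 10 of 27 under each reading.

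For one cohort of 20 in the middle scenario (4 months, 5%, 0.10), the mean 26-week shift is 1.1 points (scans stop) or 1.9 points (scans continue), against a sampling SD of about 10.6.

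A simpler set of assumptions was also run: median 3 months to progression, 12 to 24 months to progression-free death and 4 to 8 months to stopping. There, 1.6% to 4.4% of participants died on days 31 to 135 after last dose without documented progression, and median PFS stayed at 112 days throughout.

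**The case against.** The best defence is that the window is intended. Section 9.4.2 and Table 14 call the endpoint on-treatment PFS, and the DoR definition and the censoring sentence both carry the 30 days. Only the PFS definition departs from this, and inserting the window there would remove the textual conflict. That is a fair account of probable intent. It would not remove the different treatment of progression, which then becomes a choice of estimand that the plan should state. The plain label in Table 4 adds little, since that table lists short names only.

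The parenthesis in the PFS censoring sentence could grammatically cover progression as well. The DoR wording, which attaches the 30 days to death by name, makes that unlikely, and no other sentence limits progression.

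Several stronger readings are tempting and are not supported:
- A reader might infer that DoR contradicts itself too. It does not; it shares only the mismatch.
- A reader might take the statement in Appendix 13, "Every effort should be made to document objective progression even after discontinuation of treatment", as a general rule to keep scanning off treatment. In context it concerns participants who stop for symptomatic deterioration. The support for later progression counting is Section 8.1.1.
- A reader might suppose that the gap closes at the first scheduled scan, about day 56. A participant who has left the study need never have that scan, so the gap has no fixed end day.
- A reader might conclude that the rule always flatters PFS. Step 4 shows that it can do the reverse.

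The magnitudes rest on assumed rates. The top of the PFS ranges needs off-treatment progression-free death at 20 times the assumed on-treatment rate. At the lowest off-treatment rate, with scans stopping, a repeat run gave 0.1 to 1.8 points at 26 weeks and −1.4 to +1.2 at 52 weeks. The DoR shifts have no small-sample comparison, and the final futility thresholds in Section 9.5 are 3 to 5 responders of 20, so a DoR curve may rest on a handful of participants.

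**Conclusion.** The point holds. The PFS definition and its censoring sentence disagree on any progression-free death more than 30 days after last dose, and the on-treatment label does not settle which governs. Progression remains countable for nominally 105 days (75 to 135) after death stops counting, or longer if scans continue. Participants with no usable post-baseline assessment who die outside the window without documented progression have no stated handling. These findings come from the text and need no assumed rates.

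The numerical effect does depend on assumed rates. It is usually upward, can reverse, and is typically small against sampling noise in a cohort of 20. ORR, the criteria for opening Part III cohorts and the futility response counts do not change. This is a correction that should be made to secondary, descriptive endpoints; it does not threaten the primary analyses.

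**What to change.** - Make the PFS definition, the censoring sentence and Table 14 agree.
- Report one PFS analysis that counts every known death without prior documented progression as an event on its date, including deaths in participants with no usable post-baseline assessment. Keep C1D1 plus one day for those known to be alive.
- Report the 30-day version as a labelled on-treatment analysis, with the window in both its definition and its censoring sentence, and state whether the same window applies to progression.
- The sponsor chooses which version is main and says so.
- For DoR, keep the stated definition and add the all-deaths version as a sensitivity analysis.

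The cost is wording and a little programming. Deaths are already collected: Appendix 2, Section 5.1 asks for all deaths after the adverse event reporting period, and survival follow-up continues after the safety visit. Two limits apply. Section 8.11.4 ends survival updates at 24 months after initial treatment, and Section 7.2 ends follow-up when consent is withdrawn. The all-deaths estimates will be slightly less favourable in most of the scenarios examined.

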9.4.3 Safety Analyses

Unless otherwise specified, all safety analyses listed in [Table 15](#) will be based on the safety population. All safety parameters will be analyzed using descriptive statistics, summarized and presented in tables. Data will be summarized by dose and regimen (if applicable) within each part.

Table 15 Safety Statistical Analysis Methods

Endpoint	Statistical Analysis Methods
Adverse events	
The original terms recorded on the eCRF by the Investigator for AEs will be coded by the Sponsor.
 
Adverse events will be summarized by mapped term and appropriate thesaurus level. The severity of AEs will be graded according to the NCI CTCAE v5.0. Toxicity grade, seriousness, and relationship to study treatment will be presented, as well as summaries of deaths, AEs leading to death and premature withdrawal from study treatment. A glossary of AEs, medication(s), and procedures will be provided.

Clinical laboratory tests	All clinical laboratory data will be stored in the database in the units in which they were reported. Laboratory test values will be presented in International System of Units (SI units; Système International d'Unités) by individual listings with flagging of abnormal results.
Vital signs	Vital signs data will be presented by individual listings with flagging of values outside the normal ranges and flagging of abnormalities. In addition, tabular summaries will be used, as appropriate.
ECG data analysis	ECG data will be presented by individual listings. In addition, tabular summaries will be used, as appropriate.
Concomitant medications	
The original terms recorded on the participant's eCRF by the Investigator for concomitant medications will be standardized by the Sponsor by utilizing a mapped term and appropriate drug dictionary level.
 
Concomitant medications will be presented in summary tables and listings.

Nature and frequency of DLTs	DLT events will be presented by individual listings. The MTD will be estimated with an mCRM-EWOC using DLT evaluable participants. The MTD estimate will be presented along with 90% Credible Intervals.

9.4.4 Pharmacokinetic Analyses

Regular PK sampling will be performed in this study to properly characterize the PK of RO7296682 and atezolizumab.

When appropriate, PK parameters will be derived from the serum concentrations of RO7296682 using standard non-compartmental methods.

Individual and mean serum RO7296682 and atezolizumab concentration versus time data will be tabulated and plotted by dose levels and/or group, where appropriate. All PK parameters will be presented by listings and descriptive summary statistics separately by dose levels and/or dosing regimens.

Parameters may include, for example, area under the curve (AUC), clearance (CL), and volume of distribution under steady-state conditions, as appropriate. These parameters will be tabulated and summarized (mean, standard deviation, coefficient of variation, median, minimum, and maximum). Inter-participant variability and drug accumulation will be evaluated.

For RO7296682, non-linear mixed effect modeling will be used to analyze the concentration-time data. Population and individual PK parameters may be estimated, and the influence of various covariates (such as age, gender, and body weight) on these parameters may be investigated in an exploratory way. Secondary PK parameters (such as C_{max} and AUC) may be derived from the model for each participant included in the PK analysis and will be presented descriptively.

For atezolizumab, a previously developed population PK model for atezolizumab will be used to provide individual parameter estimates using Bayesian feedback methodology. Alternatively, PK data may be compared with available historical data.

Additionally, exploratory analyses on exposure and safety/efficacy relationship may be conducted if deemed necessary. The details of the modeling and exploratory analyses will be reported in a document separate from the CSR.

